3.2 SECONDARY MEASURED OUTCOMES

The following outcomes will be measured:

- The proportion of subjects with neurological death or ipsilateral stroke within the first 30 days following completion of all PHIL treatments
- Angiographic occlusion of the pre-specified target vessel intended for treatment at procedure following completion of all PHIL treatments
- New-onset or worsening of permanent morbidity at 6 month follow-up
- New-onset intracranial hemorrhage at 6 month follow-up
- New-onset of cranial nerve palsy at 6 month follow-up
- Clinically significant technical events during the PHIL embolization procedure(s) including but not limited to reflux of embolic material, migration of the embolic material, catheter entrapment or damage, and vessel dissection.
- Device-related adverse events at procedure and 30 days
- Device-related mortality at procedure and 30 days
- Procedure related adverse events including complications of arterial puncture, contrast-induced nephropathy, radiation-induced injuries, renal and anesthesia-related complications.

New-onset of device- or procedure-related neurological deficit or adverse event, or worsening of a previous neurological complaint, disorder, deficit, or adverse event that is unresolved at 6 month follow-up even if not associated with a change in mRS.Permanent morbidity is defined as a worsening of mRS score at 6 month follow-up compared to the baseline mRS score of:

- ≥1 point in subjects experiencing a stroke
- ≥2 points in subjects experiencing neurological adverse events.

Note, worsening mRS scores associated with non-neurological causes, resulting in limitations to the subject's ability to walk or require assistance to attend to own bodily needs, will not be considered permanent morbidity. This includes medical events such as, bone fractures, muscle, ligament and tendon injuries, and other physical injuries.

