5.6 PHIL PROCEDURE

Unless medically justified, the initial embolization procedure should be performed within 45 days of completion of the baseline assessment. The study procedure consists of pre-placement imaging, study device placement and post-placement imaging. Subjects require no special preparation for the procedure beyond standard of care for endovascular neuro-interventions. Investigators at their discretion may elect to pre-medicate with antiplatelet agents.

It is expected that the majority of PHIL initial and supplemental embolization procedures are completed under general anesthesia but a minority of procedures may be completed under conscious sedation, depending upon the center's standard of care. Heparin is administered according to standard practices. The PHIL device should be used per the IFU provided in the PHIL packaging. The PHIL procedure will be performed only by the physician investigator(s) trained by the Sponsor or its designee to perform the procedure.

The point of enrollment occurs when the PHIL liquid embolic syringe and adaptor assembly is connected to the microcatheter hub.

The investigator will record key characteristics of the device and procedure in the study's eCRF. The investigator will also record technical events/device malfunctions. Radiation exposure will be recorded as absorbed radiation dose and cumulative fluoroscopy time will be recorded. The investigator will retain and provide to the sponsor all images taken during or immediately after the study procedure (including any not specified above).

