7.1 PROCEDURE FOR ADVERSE EVENT REPORTING

Any medical condition that is present at the time that the subject is screened will be considered part of the subject's baseline medical history and not reported as an adverse event. However, if the subject's condition deteriorates at any time during the study, it may be recorded as an AE. Adverse events will be collected from the point of enrollment in the study until a subject exits the study.

Information to be collected includes event description, time of onset, clinician's assessment of severity, relationship to study product (assessed only by those with the training and authority to make a diagnosis), and time of resolution/stabilization of the event. AEs will be categorized using the definitions in Section 7.2. All AEs collected during the study must be followed by the Investigator until resolution or until the end of the 6 month follow-up. All applicable AEs occurring while on study must be documented appropriately regardless of the relationship.

A list of potential anticipated adverse events is provided in Section 1.3.2. AE reporting responsibilities are described in Section 7.2.

Changes in the severity of an AE will be documented to allow an assessment of the duration of the event at each level of severity to be performed.

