- Concomitant disease-related: Event is clearly attributable to the underlying concomitant disease state with no temporal relationship to the device, treatment, or medication.
- Procedure-related: Event has a strong temporal relationship to any PHIL procedure. This includes AEs attributable to any device(s) other than the PHIL™ device used at any PHIL procedure, such as access devices, delivery microcatheters, non-ionic contrast, guidewires, radiation emitting devices or any other adjunctive, approved/cleared device for treatment of intracranial dAVFs.
- Device-related: Event has a strong temporal relationship to the study device, and alternative etiology
 is less likely. The study device is the PHIL system used at any procedure including the liquid embolic
 components, adapter and syringe. All events considered "device-related" will be further characterized
 as either:
 - Anticipated: Previously identified in nature, severity or degree of incidence in the investigational plan. Or
 - Unanticipated: Not previously identified in nature, severity or degree of incidence
- Unknown: Event relationship cannot be attributed to any of the above categories and remains undetermined.

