8.2 GENERAL APPROACH

Descriptive statistics (mean, standard deviation, frequency charts, etc.) for baseline participant characteristics, subject disposition and other relevant study parameters will be reported. Where applicable, a comparison to rates reported in the scientific literature will be performed.

Tabulations of summary statistics, graphical presentations, and statistical analyses will be performed using SAS software version 9.2 or higher. The statistical analyses will be based on data pooled across sites in aggregate. All subset summary tables and data listings will be sorted by site and subject. The pre-procedure observations will be used as the baseline value for calculating post-procedural changes from baseline.

Continuous demographic parameters, such as the age of the subject at the time of enrollment, will be summarized using descriptive statistics (N, mean, median, standard deviation, minimum and maximum value). Categorical demographic parameters, such as gender, will be summarized as a proportion of the population.

Data obtained during the neurological examination using the Modified Rankin and self-reported EQ-5D will be summarized at each time point using descriptive statistics.

Routine clinical chemistry and hematology will be assessed by the investigator as normal/abnormal and not clinically significant/clinically significant. The incidence of abnormal and clinically significant values will be summarized and reported in frequency tables for each visit at which the data are collected.

Subject counts will be tabulated for all adverse events for the population. Adverse events will also be tabulated for events that occurred at procedure and at 6 month follow-up after last embolization. Tabulated subject counts will be presented as a proportion of the population.

All recorded data will be presented in the individual data listings.

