15 DEFINITIONS

Term	Definition
Adjunctive treatment Adverse Event (AE)	Additional treatments with to continue or complete the treatment of the fistula
	other than PHIL. This could include but is not limited to other liquid embolic agents embolic coils, surgery or radiosurgery.
	Any untoward medical occurrence, unintended disease or injury, or untoward
Adverse event (AE)	clinical signs (including abnormal laboratory findings) in subjects, users or other
	persons, whether or not related to the investigational medical device. (ISC 14155:2011 3.2)
	NOTE 1: This definition includes events related to the investigational medical device
	or the comparator.
	NOTE 2: This definition includes events related to the procedures involved.
	NOTE 3: For users or other persons, this definition is restricted to events related to
	investigational medical devices.
Completion of treatment	Cessation of blood flow through all the vessels targeted for embolization, as specified by treating physician in eCRF.
Concomitant disease-related adverse event	Event is clearly attributable to the underlying concomitant disease state with no
	temporal relationship to the device, treatment, or medication.
Device-related adverse event	Event has a strong temporal relationship to the study device, and alternative
	etiology is less likely.
Enrolled	Subject has provided written informed consent to participate in the study, meets
	all enrollment criteria, and treatment with the PHIL device is attempted. The point
	of enrollment occurs when the PHIL liquid embolic syringe and adaptor assembly is
	connected to the microcatheter hub.
Full Analysis Set Population (FAS)	All enrolled subjects including only those in whom the PHIL™ device was implanted.
NIH Stroke Scale (NIHSS)	Tool to quantify neurological impairment caused by stroke.
Intracranial hemorrhage	Hemorrhage within the fixed vault of the cranium (skull)
Mild	No limitation of usual activities, no therapy or only symptomatic therapy required
(AE severity)	to treat the injury or illness.
Moderate	Some limitation of usual activities or specific therapy is required.
(AE severity)	Some illitation of assault activities of specific therapy is required.
Modified Rankin Scale (mRS)	Scale for measuring general neurologic function.
,	0 No symptoms at all
	1 No significant disability despite symptoms; able to carry out all usual duties
	and activities
	2 Slight disability; unable to carry out all previous activities, but able to look

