## 8. Statistical Analysis Methodology

### 8.1 General Statistical Approach

Descriptive statistics (mean, standard deviation, frequency charts, etc.) for baseline participant characteristics, subject disposition and other relevant study parameters will be reported. Where applicable, a comparison to rates reported in the scientific literature will be performed.

Tabulations of summary statistics, graphical presentations, and statistical analyses will be performed using SAS. The statistical analyses will be based on data pooled across sites in aggregate. All subset summary tables and data listings will be sorted by site and subject. The pre-procedure observations will be used as the baseline value for calculating post-procedural changes from baseline.

Continuous demographic parameters, such as the age of the subject at the time of enrollment, will be summarized using descriptive statistics (N, mean, median, standard deviation, minimum and maximum value). Categorical demographic parameters, such as gender, will be summarized as a proportion of the population.

Data obtained during the neurological examination using the Modified Rankin and self-reported EQ-5D will be summarized at each time point using descriptive statistics.

Routine clinical chemistry and hematology will be assessed by the investigator as normal/abnormal and not clinically significant/clinically significant. The incidence of abnormal and clinically significant values will be summarized and reported in frequency tables for each visit at which the data are collected.

Subject counts will be tabulated for all adverse events for the population. Adverse events will also be tabulated for events that occurred from the start of the procedure to 6 month follow-up after last embolization. Tabulated subject counts will be presented as a proportion of the population.

All recorded data will be presented in the individual data listings.

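### Protocol 7.1 opens adverse-event collection at PHIL hub connection, after the procedure has begun, although SAP 8.1 counts from procedure start and the outcome names puncture and anesthesia complications

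*Protocol*

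**What the plan says.** The collection window is set in Protocol 7.1: "Adverse events will be collected from the point of enrollment in the study until a subject exits the study". Protocol 5.6 fixes when enrollment happens: "The point of enrollment occurs when the PHIL liquid embolic syringe and adaptor assembly is connected to the microcatheter hub". Section 15 gives the same definition.

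The tabulation window is in SAP 8.1: "Adverse events will also be tabulated for events that occurred from the start of the procedure to 6 month follow-up after last embolization". The SAP does not define the start of the procedure.

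The outcome concerned is in Protocol 3.2, and is repeated in Protocol 7 and SAP 8.3: "Procedure related adverse events including complications of arterial puncture, contrast-induced nephropathy, radiation-induced injuries, renal and anesthesia-related complications". Protocol 7.2.1 defines a procedure-related event broadly: "Event has a strong temporal relationship to any PHIL procedure". It extends this to events caused by access devices, guidewires, contrast and delivery microcatheters.

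Section 4 of the protocol uses 'enrolled' in an earlier sense. It covers subjects who fail the pre-operative criteria and never receive PHIL.

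**The concern.** The rule for collecting events starts later than the procedure whose complications are to be counted. A site that follows 7.1 to the letter could leave out a puncture or anesthesia complication that began before the syringe was attached, and would be complying with the protocol. Because the rate is descriptive and may be set beside literature rates (Protocol 8.2, SAP 8.1), the numerator should not depend on how each of up to 25 sites reads 7.1. The only possible direction of error is toward fewer reported complications.

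**Working it through.** The plan gives no figure to reproduce on this point. The check compares start points, then sizes the effect of one missed subject.

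1. **Start points side by side.**
   - Collection (Protocol 7.1 with 5.6 and Section 15): attachment of the PHIL syringe to the hub.
   - Content of the procedure (Protocol 5.6): imaging before placement, then placement, then imaging afterwards. It therefore begins before attachment.
   - Procedure clock (Section 15, procedure time): the first fluoroscopic or angiographic acquisition, also before attachment.
   - Late screening failures (Protocol 5.5.2): a subject can be excluded during the study procedure because the microcatheter cannot reach the lesion. The procedure can thus be running in someone not yet enrolled.
   - Tabulation (SAP 8.1): procedure start, undefined.

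2. **What can fall in the gap.** A microcatheter must be in place before anything is attached to its hub, so arterial access comes first. Protocol 5.6 expects general anesthesia in most procedures. Some puncture and anesthesia complications can therefore begin before attachment. Contrast nephropathy, radiation injury and renal complications are likely to appear afterwards. No text gives onset times, so the share in the gap is unknown. Nor does any text say that anesthesia or puncture follows the first image acquisition, so the Section 15 clock may itself start too late to cover them.

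3. **First versus supplemental procedures.** Enrollment happens once. At a supplemental procedure the subject is already enrolled, so the same early event is inside the window. No reason is given for treating the two differently.

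4. **Where an event could be lost.** SAP 8.5 computes study day from dates. For an event on the day of the index procedure, (event date − deployment date) + 1 = 0 + 1 = 1, whether it began before or after attachment. A recorded event is therefore kept. Loss can occur only when a site decides whether to record it.

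5. **Who could be affected.** The rate changes only for a subject in the Full Analysis Set whose event began before attachment at the first procedure, was not recorded, and who had no other counted procedure-related event. A subject in whom PHIL was never connected is not enrolled, so is outside the Full Analysis Set under either start point.

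6. **Size per subject.** With N = 75, one subject is 1/75 = 1.33 percentage points. Clopper-Pearson two-sided 95% limits, the SAP's method:
   - 0/75: 0 to 1 − 0.025^(1/75) = 4.80%.
   - 1/75 = 1.33%: 0.03% to 7.21%.

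7. **Primary outcomes.** The primary safety window runs from completion of the first procedure, which is later than attachment. The primary benefit outcome is an angiographic finding at the procedure. Neither depends on when adverse-event collection opens, beyond a negligible effect.

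**The case against.** The strongest reply is that other text already calls for these events. The schedule (Table 6) marks adverse events at the PHIL procedure. Protocol 7.1 adds: "All applicable AEs occurring while on study must be documented appropriately regardless of the relationship". Table 7 in 5.16 makes incomplete measured outcome data a major deviation. Protocol 3.2 lists vessel dissection among technical events during the procedure, with no enrollment-based start, although 7.2.2 defines a technical event more narrowly. Monitors compare source documents with case report forms (5.17.1.4), and an independent committee adjudicates primary and secondary outcomes (7.4). All this makes omission less likely, and that part stands. But none of it sets an earlier start. The schedule names a visit, being on study is not defined, monitors check against the protocol as written, and adjudicators see only what is reported. The earlier sense of 'enrolled' in Section 4 would open the window sooner, but it contradicts 5.6 and Section 15.

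It is also fair that the SAP mismatch removes nothing in the analysis: a tabulation window wider than the collection window drops no recorded event.

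Three stronger readings are tempting and not supported.
- A reader might infer that many of the named complications begin before attachment. No document gives onset times.
- A reader might scale up Protocol Table 5. Pooling femoral dissection (1), groin hematoma (2) and bradycardia (1) gives 4/750, or 0.4 of 75 subjects. Single series give 2/150, or 1.0 of 75, and 1/12, or 6.25 of 75. The spread shows how little this says. The table gives no timing, and calling bradycardia an anesthesia event is the reader's own label.
- A reader might see a further conflict in Protocol 8.2: "Adverse events will also be tabulated for events that occurred at procedure and at 6 month follow-up after last embolization". That wording is looser than SAP 8.1 but does not contradict it on the start point.

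**Conclusion.** The inconsistency is real and rests on the text alone. The stated collection rule opens after the procedure has begun, while a named secondary outcome and SAP 8.1 both reach back to events that may come earlier. Followed literally, it can give too low a count at the first procedure.

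The consequence is minor. It touches one descriptive secondary rate, with no hypothesis test. The bias can only be downward, by 1.3 points per uncounted subject on the assumption that 75 subjects are evaluated. How many subjects are affected cannot be derived and may be zero. A reader might infer that events have in fact been missed; nothing in the documents shows that.

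**What to change.** - In Protocol 7.1, state that for consented subjects adverse events are collected from the start of the first PHIL procedure.
- Define that start once, so that it covers the anesthesia and arterial-access complications named in the outcome, and use the same start in SAP 8.1.
- Use 'enrolled' in one sense in Sections 4, 5.6 and 15.
- New wording recovers nothing for first procedures already performed. Protocol Revision A dates from January 2018 with about 36 months of enrollment planned, and Revision E from April 2023, so there may be many; the documents do not give enrollment status. For these, check existing source records for unrecorded events that began before the syringe was attached, or state the limitation in the study report.

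The wording change costs one sentence in 7.1 with matching edits elsewhere, a few more adverse-event forms, and possibly a slightly higher reported rate. The source check adds some site and monitoring time; stating the limitation instead costs almost nothing.

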7.2 Reporting events

Safety events must be reported to the Sponsor in a timely manner. The primary method of reporting events will be through the eCRFs. If the database is unavailable, the investigator may send the information to the study team. As soon as the database becomes available, the investigator must complete data entry. The investigator will send all available supporting documentation (blinded/de-identified as to the subjects' identity) to the Sponsor.

As additional information becomes available, copies of that source documentation which contain significant information related to the event such as progress notes, consultations, nurse's notes, operative reports, imaging studies and subject summaries etc. are requested for a complete evaluation of the event.

Regarding subject deaths, it is requested that a copy of the death certificate and a copy of the autopsy report, if applicable, be sent to the Sponsor when available. Any other source documents related to the death should also be provided to the Sponsor. If no source documents are available, the PI is requested to describe the circumstances of the subject's death in a letter, e-mail or other written communication. The Sponsor will report all deaths on an interim basis to FDA, as they are reported by the PI.

UADEs/USADEs have expedited reporting requirements. The investigator is required to report any UADEs/USADE's to the Sponsor as soon as possible (i.e. within 24 hours) but no later than 10 working days after first learning of the event. The Sponsor is required to report any event that meets the definition of Unanticipated Adverse Device Effect (Section 7.2) to FDA, all investigators and reviewing IRBs within 10 working days after becoming aware of information that an unanticipated adverse device effect has occurred. The site will notify the reviewing IRB within 10 working days after becoming of aware of the effect.

7.2.1 DEFINITIONS

An **Adverse Event** (AE) is defined as any untoward medical occurrence, unintended disease or injury, or untoward clinical signs (including abnormal laboratory findings) in subjects, users or other persons, whether or not related to the investigational medical device. (ISO 14155:2011 3.2)

- NOTE 1: This definition includes events related to the investigational medical device or the comparator.
- NOTE 2: This definition includes events related to the procedures involved.
- NOTE 3: For users or other persons, this definition is restricted to events related to investigational medical devices.

A **Serious Adverse Event** (SAE) is defined as an adverse event that

- a) Led to death,
- b) Led to serious deterioration in the health of the subject, that either resulted in
 - i. A life-threatening illness or injury, or
 - ii. A permanent impairment of a body structure or a body function, or
 - iii. In-subject or prolonged hospitalization, or
 - iv. Medical or surgical intervention to prevent life-threatening illness or injury or permanent impairment to a body structure or a body function,
- c) Led to fetal distress, fetal death or a congenital abnormality or birth defect (ISO 14155:2011 3.37)

NOTE: Planned hospitalization for a pre-existing condition, or a procedure required by this protocol, without serious deterioration in health, is not considered a serious adverse event.

An **Unanticipated Adverse Device Effect** (UADE) is defined as any serious adverse effect on health or safety or any life-threatening problem or death caused by, or associated with, a device, if that effect, problem, or death was not previously identified in nature, severity, or degree of incidence in the investigational plan or application (including a supplementary plan or application), or any other unanticipated serious problem associated with a device that relates to the rights, safety, or welfare of subjects. (21 CFR 812.3 (s))

Severity:

- Mild: No limitation of usual activities, no therapy or only symptomatic therapy required to treat the injury or illness.
- Moderate: Some limitation of usual activities or specific therapy is required.
- Severe: Inability to carry out usual activities, hospitalization, emergency treatment, life threatening events, or death.

Relatedness:

• Study Disease-related: Event is clearly attributable to the underlying study disease state with no temporal relationship to the device, treatment, or medication.

- Concomitant disease-related: Event is clearly attributable to the underlying concomitant disease state with no temporal relationship to the device, treatment, or medication.
- Procedure-related: Event has a strong temporal relationship to any PHIL procedure. This includes AEs attributable to any device(s) other than the PHIL™ device used at any PHIL procedure, such as access devices, delivery microcatheters, non-ionic contrast, guidewires, radiation emitting devices or any other adjunctive, approved/cleared device for treatment of intracranial dAVFs.
- Device-related: Event has a strong temporal relationship to the study device, and alternative etiology
 is less likely. The study device is the PHIL system used at any procedure including the liquid embolic
 components, adapter and syringe. All events considered "device-related" will be further characterized
 as either:
 - Anticipated: Previously identified in nature, severity or degree of incidence in the investigational plan. Or
 - Unanticipated: Not previously identified in nature, severity or degree of incidence
- Unknown: Event relationship cannot be attributed to any of the above categories and remains undetermined.

